Affected Subjects: Adolescents (ages 9-21 years) with a current DSM-IV-TR diagnosis of MDD or Depressive Disorder NOS (defined as exhibiting 4 of 5 criteria for an episode of major depression or meeting all MDD criteria except duration) will be recruited from the University of Cincinnati BITREC “at-risk” cohort (n=140, UC-IRB #07-04-10-03) of adolescent offspring of parents with bipolar I disorder. To be included in the BITREC at-risk cohort, adolescents must have no lifetime syndromal mood or psychotic disorder at their initial baseline assessment, a parent with bipolar I disorder, and no contraindication to undergoing an MRI scan. Based on data from prior studies we estimate that at least 35% of the cohort will develop MDD within the 5-year longitudinal follow-up period of BITREC.⁶ Subjects for the proposed study will be recruited from the “at-risk” cohort as well as from adolescents who have already developed MDD or Depressive Disorder NOS and who are screen failures for the BITREC “at-risk” cohort. The BITREC at-risk adolescents in the BITREC are evaluated monthly for follow-up and are instructed to call study staff between visits if mood symptoms emerge, so that we will be able to identify potential subjects for the proposed study at or soon after the onset of a mood disorder. If a subject is recruited from outside of BITREC, their biological parent(s) with bipolar I disorder will be asked to complete a Structured Clinical Interview for DSM Disorders (SCID) to confirm diagnosis of bipolar I disorder. One of the main goals of BITREC is to identify neurobiological changes that occur prior to and at the onset of a mood disorder in adolescents who have a parent with bipolar I disorder. Therefore, all at-risk adolescents who develop a mood disorder will undergo a ¹H MRS as part of their participation in the BITREC, which is identical to the MR scans proposed for this study. This scanning session will occur during the baseline study visit for the proposed study for eligible BITREC subjects who choose to participate in the proposed trial. The omega-3 treatment trial and the week 12 MRS scan will occur exclusively as part of this study and are distinct from, although complementary to, participation in the BITREC. As part of the BITREC longitudinal illness course assessments are performed in the at-risk adolescents. However, the BITREC does not include a systematic treatment study for these individuals, other than for those who develop mania, who will be excluded from participation in the proposed study. We will give all participants the opportunity to participate in BITREC at study termination in order to provide follow-up.

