Two-week and Long-term Follow-up: At the end of the 12 weeks patients and their legal guardians (if < 18 years) will decide whether they would like to continue (or start for those receiving placebo) omega-3 fatty acids. Regardless of the treatment chosen, all patients will return for a follow-up visit two weeks following their last visit in the DBPC study to ensure that there has been no significant worsening of their mood. Importantly, all patients will have the option to continue to participate in the BITREC, which is a longitudinal 5-year study. Since some patients will opt to continue omega-3 fatty acid treatment, this will permit us to obtain long-term effectiveness and tolerability data. Safety and efficacy assessments will be performed at all follow-up visits. Subjects will be responsible for obtaining their own omega-3 fatty acids supplementation after study completion if they wish to continue with omega-3 treatment. Omega-3 fatty acids are widely available via food, health, and supplement retail stores at a relatively low cost.

Assessments:

The Children's Depression Rating Scale-Revised (CDRS-R), a 17-item observer-rated questionnaire,^{40,41} and the

Young Mania Rating Scale (YMRS),⁴²⁻⁴⁴ an 11-item observer-rated questionnaire to assess depressive and manic symptoms, respectively. A consensus adolescent/legal guardian score for the CDRS-R and YMRS will be determined by the rater.

Subjects will also be rated using the Clinical Global Impression-Severity Scale (CGI-S), a clinician rated 7-point scale (rated from 1=normal to 7=extremely ill) to assesses overall illness severity.⁴⁵ CDRS-R, YMRS, and CGI-S will be administered at screening, baseline (concurrent with the first imaging session) and then subsequently at each weekly follow-up visit and will be used to rate symptoms during the prior week.

The CGI-Improvement Scale (CGI-I) is a clinician rated scale that assesses overall illness change

from baseline and will be administered at all post-baseline visits.

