Image acquisition and fMRI: fMRI evaluations will be obtained on subjects at the baseline visit and at 12 weeks. All subjects will be scanned at the University of Cincinnati College of Medicine's Center for Imaging Research (CIR) using a 4.0 Tesla Varian Unity INOVA Whole Body MRI/MRS system (Varian Inc., Palo Alto, CA). The INOVA system is controlled by a SUN workstation running Varian's VNMR-JTM and SPIN-CADTM image processing and pulse-sequence development software under a Unix-based operating system. Data are stored on a networked hard drive (for off-line analysis) and additionally backed up by burning onto CDs or DVDs.

During the scan sessions, subjects recline in a supine position on the scanner bed. Nonferromagnetic goggles are positioned to provide clear visualization of the stimuli and a radio-frequency (RF) coil is placed over the subject's head. Padding is inserted around the subject's head to minimize movement. Headphones are provided to block background noise and so that investigators can communicate with the subjects during scan acquisition. A microphone in the scanner permits subjects to communicate with the MRI technician in case of concern or discomfort.

Following a three-plane gradient echo scan for alignment and brain localization, a shim procedure is performed to generate a homogeneous magnetic field. To provide anatomical localization for activation maps, a high-resolution, T1-weighted, 3-D brain scan is obtained using a modified driven equilibrium Fourier transform (MDEFT) sequence ($T_{MD}=1.1$ s, $TR=13$ ms, $TE=6$ ms, $FOV=25.6 \times 19.2 \times 19.2$ cm, matrix $256 \times 192 \times 96$ pixels, flip angle=20 degrees). A midsagittal localizer scan is obtained to place 40 contiguous 4 mm axial slices that extend from the inferior cerebellum to encompass the entire brain. Subjects then complete an fMRI session in which scans

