Spectral Analysis: We have implemented a spectral fitting routine that uses an iterative, non-linear, Marquardt-Levenberg algorithm in combination with prior spectral knowledge to precisely fit acquired spectra. The spectral model allows for the inclusion of various constraints in the spectral model such as spectral linewidths, phase/frequency offsets and lineshapes. The model template will be iteratively fitted to the raw data until the minimum residual (within an acceptable level of tolerance) between the raw and modeled data is reached. The fitting algorithm accounts for both zeroth- and first-order phase, thus alleviating the need for prior filtering, Fourier-Transformation and phase-correction of the data. If the spectrum from an entire anatomical structure is to be studied, multiple spectra can be collected and summed from the structure of interest. For maximal signal coherence, each spectra will first be corrected for zeroth-order phase shifts resulting from point-spread effects, as well as for frequency shifts resulting from B₀ inhomogeneity, prior to summing.

b. Data Analyses and Data Monitoring:

Data Analyses

Prediction 1: Omega-3 fatty acid supplementation will be more effective than placebo for the treatment of mood symptoms in adolescents with a high risk for developing mania. A mixed effects model repeated measures (MMRM) approach will be used to compare change over time in CDRS-R (and YMRS) scores between treatment (omega-3 vs. placebo) groups. Covariates for these models will be time of assessment (study week) and treatment group. A mixed model approach will account for missing information while adjusting for the correlation of observations over time. We will also use MMRM to compare change over time in total mood burden rating. We will evaluate other potential covariates and confounds as described and will specifically examine the effects of co-occurring ADHD and anxiety disorders, and concomitant use of stimulants within groups. We will also compare treatment group differences in change from baseline to endpoint in YMRS and CDRS-R scores using an analysis of variance (ANOVA). This analysis will provide information without the necessary assumptions of the MMRM model regarding missing data and fitting the regression. We will calculate the effect sizes of group differences for change in CDRS-R and YMRS using the formula $d = (\text{mean change from baseline to endpoint group 1} - \text{mean change from baseline to endpoint$

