Prediction 3: Omega-3 fatty acids will be safe and well tolerated compared with placebo. To evaluate the safety and tolerability of omega-3s we will use ANOVAs to compare change from baseline to week 12 (or endpoint) in vital signs and laboratory values. Additionally, we will determine the percentage of subjects who reported each adverse event and will examine treatment group differences in adverse events and serious adverse events using Fisher exact or χ^2 tests.

Prediction 4: Improvement in mood symptoms following treatment with omega-3 fatty acids is mediated by decreases Glu and mI levels and increases in NAA levels in the VLPFC (BA 10) and ACC (BA 24, 32). Our hypothesized model predicts that treatment produces changes in metabolite levels (Glu, mI, and NAA). These metabolite changes lead to change in mood symptoms. The mediated link between treatment and mood symptoms via metabolite levels is the *indirect treatment effect*. The *direct treatment effect* represents any residual association between treatment and mood symptoms after adjusting for the *indirect effect*. This association will be smaller in magnitude than the unadjusted association between treatment and mood symptoms (which is the *total treatment effect* or the quantity of interest in Prediction 1). For the prediction of a mediated treatment effect to be supported, two conditions must be met, i.e., significant associations between treatment and metabolite levels and between metabolite levels and mood symptoms. Prediction 4(a) is that treatment with omega-3 fatty acids will lead to decreases in Glu and mI levels and increases in NAA levels within VLPFC and ACC. It is possible for this prediction to be supported in the absence of a general association between treatment and mood symptoms (Prediction 1), which would suggest that these metabolic changes do not impact clinical outcome. Prediction 4(b) is that decreases in Glu and mI levels in VLPFC and ACC, and increases in NAA in VLPFC and ACC, will lead to decreases in

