mood symptoms. It is possible for this prediction to be supported in the absence of a general association between treatment and mood symptoms (Prediction 1), which would suggest that these metabolic changes impact clinical outcome but are not induced by omega-3 fatty acids (i.e., they are a treatment-independent marker for clinical improvement). If both components of Prediction 4 are supported, it will be of further interest to assess the extent of mediation: If the direct (i.e., residual) treatment effect is not statistically significant, the data are consistent with *complete mediation* (i.e., the treatment effect on mood is fully accounted for by the intermediate effect on metabolite levels). If other effects of treatment on mood symptoms not specified by this model exist, the direct (i.e., residual) treatment effect may remain significant and the data would be said to support *partial mediation*. Path analysis⁸², which for linear models is a decomposition of the linear covariance matrix of the variables, will be used to analyze the fit of the proposed mediation model to our data. Path analysis can be thought of as an extension of linear regression to systems of simultaneous linear regression equations. This allows for the same variable to serve as an independent variable in some of the regressions and a dependent variable in others. In this study, changes in metabolite levels assume both roles: They are dependent variables in prediction 4(a) and independent variables in prediction 5(a). CDRS-R scores as well as other pilot mood measures will serve as the final outcome measures, with changes in metabolite levels as mediators and treatment group as an independent variable. Estimation of all the path coefficients, along with bootstrap computation of associated standard errors and significance levels (adjusted $\alpha=0.017$ to control for multiple testing) will be carried out using the SAS macros,⁷⁸ which are available for download at [http://www.comm.ohio-state.edu/ahayes/SPSS% 20programs/indirect.sas](http://www.comm.ohio-state.edu/ahayes/SPSS%20programs/indirect.sas). We also will examine the effect of metabolite changes on behavioral symptoms (ADHD-RS scores), functional ratings and the pilot mood burden scale on these models in a set of expanded path models. The Bayesian Information Criterion (BIC) will be used to assess the goodness of fit of different path models to the data. This model comparison statistics combines the likelihood of the data with a penalty term that adjusted for the number of parameters used to fit the data. This statistic can be used to rank the mediation model against simpler models where one or both of the components of Prediction 4 are assumed to be absent, or where these paths are supported with respect to some metabolites but not others. Another comparison of interest (though secondary to our aims) is to compare the full path model (which shows partial mediation, since a path representing residual treatment effect is included) to a complete mediation model which does not have a direct path from treatment to mood symptoms (implying that the correlation between treatment and mood symptoms, after accounting for metabolite levels, is zero). If both of the paths involving metabolite levels are null, but the correlation between treatment and mood symptoms is significant, the path model reduces to simple linear regression (i.e., a t-test, since the independent variable is binary). Comparison of overall model fit with BIC is important since a model in which the paths for predictions 4(a) and 4(b) fall somewhat close to significance, (e.g., $p=0.05$ for each path) may still give a better overall fit to the data than a model that omits both of these paths.

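### With scans only at baseline and week 12, the mediation rule (Predictions 4 and 5) cannot establish that metabolite change drives mood change, yet it is written as if it could

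*Combined protocol and SAP*

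**What the plan says.** **Timing.** The schedule of assessments (Figure 1) places ¹H-MRS at baseline and week 12 only. Section E.a, Affected Subjects, agrees. For BITREC participants, "This scanning session will occur during the baseline study visit for the proposed study for eligible BITREC subjects", and "The omega-3 treatment trial and the week 12 MRS scan will occur exclusively as part of this study". Mood is rated at "baseline (concurrent with the first imaging session) and then subsequently at each weekly follow-up visit" (Assessments).

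**Mood interval.** The path-model text names no interval for mood change. For Prediction 1 the plan will "compare treatment group differences in change from baseline to endpoint in YMRS and CDRS-R scores". Baseline to week 12 is also the only span over which a metabolite change exists.

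**Rule.** Prediction 4 starts from a hypothesized model: "These metabolite changes lead to change in mood symptoms". For that prediction to be supported, two conditions must be met: "significant associations between treatment and metabolite levels and between metabolite levels and mood symptoms". There is no condition on time order or confounding. If 4(b) holds without a treatment effect on mood, the plan's reading is "which would suggest that these metabolic changes impact clinical outcome but are not induced by omega-3 fatty acids". A parenthesis in the same sentence then describes the metabolites as a marker of improvement that does not depend on treatment. Prediction 5(b) repeats the directional wording within the omega-3 arm.

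**Model comparison.** BIC ranks the mediation model against versions with paths removed or restricted to some metabolites. No reverse-order or common-cause model is listed.

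**The concern.** Three structures give a within-arm association between metabolite change and mood change: metabolites move mood, mood moves metabolites, or something else moves both (sleep, adherence, diet or natural recovery, for example). When both changes are taken over the same 12 weeks, the association alone cannot tell them apart.

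Randomization protects the effect of treatment on metabolites (4a) and the total effect on mood. It does not protect the metabolite-to-mood path in 4(b) or 5(b). In Prediction 5 the exposure, RBC change within one arm, is not randomized either.

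At stake is the mechanistic conclusion of Aim 2. A consequence of improvement, or a correlate of it, could be reported as the mechanism of benefit. The efficacy comparison in Prediction 1 and the safety analyses are not affected.

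**Working it through.** The plan states no figure that this point should reproduce. The check asks how often the two-condition rule is met when there is no mediation.

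**Inputs from the documents**
- 30 per arm, with about 25% lost or without usable MRS (section F.2): 60 × 0.75 = 45 evaluable, so 22 to 23 per arm.
- Alpha 0.017 per path (Prediction 4), which matches 0.05/3 = 0.0167.
- Effect sizes of interest d = 0.6 to 0.8 (section F.2).

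**Assumptions, not in the documents**
- Within-arm mood-metabolite correlation r from 0.3 to 0.7.
- One metabolite, unit variances, and t-tests in place of the planned bootstrap.

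**Step 1: reverse-order model.** Let mood change be Y = d·T + e₁ and metabolite change M = r·Y + √(1−r²)·e₂. Treatment acts on mood, and mood acts on the metabolite. The treatment effect on the metabolite is then r·d on a residual SD of 1.

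**Step 2: condition 4(a).** With 22 per arm the noncentrality is r·d·√(22/2), and the critical t on 42 df at two-sided 0.017 is 2.486. For r=0.6 and d=0.8 this is 0.48 × 3.317 = 1.592, giving power of about 20%.

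**Step 3: condition 4(b).** This tests M in the regression of Y on T and M. Its power depends on r, not on d. At r=0.6 it is 98%. The product, 0.198 × 0.98 ≈ 0.19, agrees with the simulated 19.0%.

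**Step 4: both conditions.** Simulation with 20,000 replicates per cell:

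| r | 4(b) significant | both met, d=0.6 | both met, d=0.8 |
|---|---|---|---|
| 0.3 | 34% | 1.0% | 1.6% |
| 0.4 | 62% | 3.3% | 5.1% |
| 0.5 | 87% | 6.5% | 11.3% |
| 0.6 | 98% | 10.5% | 19.0% |
| 0.7 | about 100% | 14.7% | 27.7% |

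Separate runs of 4,000 to 6,000 replicates with 22 or 23 per arm agree to within about 1 to 2 percentage points.

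**Step 5: does 4(b) depend on the direction?** With no treatment effect, 23 per arm and r=0.5, 4(b) is significant in 88.9% of trials if metabolites drive mood, 88.8% if mood drives metabolites, and 88.4% under a common cause. At r=0.3 the figures are 35.4%, 35.1% and 34.0%.

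**Step 6: can BIC decide?** The full forward model factors the joint distribution as p(M|T)·p(Y|T,M), and the full reverse model as p(Y|T)·p(M|T,Y). Both equal p(M,Y|T) and have the same number of parameters, so likelihood and BIC are identical. In simulation the difference stayed below 10⁻¹³. Only the chains without a direct path can differ. At r=0.6, among trials that wrongly met both conditions, the reverse chain fitted as well or better in about 67% at d=0.8 and 52% at d=0.6. A third to a half of the false mechanisms would therefore survive that screen.

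**The case against.** **The plan is not uniformly causal.** This stands. Aim 2 speaks of potential mediators, and Aim 1 calls the data pilot data. The *lead to* sentence follows the announcement of a hypothesized model. Complete mediation is already phrased as something the data are *consistent with*. The sentence on 4(b) ends with the marker reading. A reader might infer that the plan asserts causation throughout, and the documents do not support that. The defect is narrower: *impact* and *marker* are different claims joined in one sentence, and the formal rule for support still rests on two associations.

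**The reverse direction is explored.** Partly so. The exploratory analyses look at effects of change in behavioral, functional and pilot mood burden measures on metabolite change. They do not name CDRS-R or YMRS, run at 0.05, and do not enter the rules for Predictions 4 or 5.

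**The error rates are modest.** This also stands. A reader might take the 98% for 4(b) at r=0.6 as a false-positive rate. It is power to detect a real correlation. What is wrong is the interpretation attached to that correlation. The rate that matters is for both conditions together, and it is small at low correlations.

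**Weekly or week 14 mood ratings could supply the order.** Weekly ratings do not help without metabolite values between the two scans. The week 14 rating follows the last scan, but treatment after week 12 is by choice and no lagged analysis is planned. Section G.3.d mentions an MRI at a week 16 visit. That conflicts with the 14-week schedule and should be reconciled, but it adds no mid-treatment scan.

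**Conclusion.** The concern holds. Followed as written, the rule in Prediction 4 can call mediation supported, and the text can describe metabolites as affecting outcome, when the data cannot separate that from the reverse order or a common cause. The same applies to 5(b).

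If mood drives metabolites, the rule is met wrongly in about 1 to 15% of trials at d=0.6 and about 2 to 28% at d=0.8. These ranges rest on assumed correlations of 0.3 to 0.7, one metabolite, 22 per arm and normal-theory tests. They also take mood change over baseline to week 12, which is inferred because the path-model text does not state it.

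Two stronger readings are not supported. The treatment-to-metabolite comparison in 4(a) is not undermined, because it is randomized. And a false mechanism is not the expected result: under these assumptions it is a minority outcome. The change should be made because the conclusion belongs to a main aim and the correction is nearly free.

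**What to change.** 1. In Predictions 4 and 5, restate the rule so that meeting both conditions is reported as compatible with mediation, direction not established.
2. Describe 4(b) and 5(b) as associations. Delete *impact* from the interpretation, keep the marker reading, and present *lead to* only as the hypothesis.
3. State that a mediation reading assumes metabolite change precedes mood change and that no unmeasured factor confounds the two. Name the mood-change interval used in the path model.
4. Report a sensitivity analysis to correlation between the mediator and outcome residuals. In the single-metabolite model, the residual correlation that brings the path to zero is the observed treatment-adjusted correlation between the two changes, so the tipping point is easy to give.
5. Do not let BIC against a reverse-order model decide direction. A rule that allowed mediation only when the reverse model fits worse would never allow it for the full model. If a reverse model is shown, report the tie as evidence that direction is not identified.

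The cost is a more modest Aim 2 claim, some SAP wording and one small analysis. No extra scans or patients are needed. Establishing time order would need a mid-treatment scan, which this fix does not require.

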
even the direction) of an association between two variables to depend on the levels of moderating variables. We will assess moderation by the magnitude of the interaction terms in an ANCOVA model where change in mood symptoms is the outcome and the predictors are treatment group, change in metabolite levels, and interactions between metabolite changes and treatment group. A moderated relationship would be consistent with a pattern of results where an association between metabolite levels and mood symptoms exists in the omega-3 fatty acid group, but not in the placebo group. Such an outcome is plausible because placebo response may occur due to mechanisms that are independent of those we hypothesize as causes of treatment response.

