Patients: This is a 12-week double-blind randomized investigation of omega-3 fatty acid (N=30) vs. placebo (N=30) for the treatment of major depressive disorder and depressive disorder NOS in adolescents (N_{Total}=60). Patient selection will be done by research staff in consultation with and with permission from the PI. Inclusion/Exclusion criteria are found below (see F., 3.).

Healthy Controls: Although we will not recruit healthy subjects for the proposed study, they are recruited (n=40) already for BITREC Project 3 and undergo an initial ¹H-MRS scan. Therefore, we will be able to interpret the direction of neurobiological changes in at-risk adolescents (i.e., whether patient values are changing toward or away from those of healthy adolescents).

2. Estimated sample size: We propose to randomize 30 subjects per treatment group, for a total of 60 subjects at the University of Cincinnati. As this is an investigator-initiated protocol, there are no other sites associated with this submission.

Based on our prior studies, we estimate that approximately 25% of patients will either discontinue study participation prior to completing study procedures or will not have usable MRS data. For the power calculations described, we considered medium to large effect sizes of $d > 0.6-0.8$ to be clinically relevant.⁷⁹

3. Description of Inclusion/Exclusion Criteria

Inclusion Criterion:

- Ages 9 -21 years old.
- At least one biological parent with bipolar I disorder.
- Meets DSM-IV-TR⁸⁰ criteria for major depressive disorder (MDD) or Depressive Disorder NOS at screening as determined by the Washington University at St. Louis Kiddie Schedule for Affective Disorders and Schizophrenia, WASH-U-KSADS;⁸¹
- Childhood Depression Rating Scale-Revised Version^{40,41} (CDRS-R) scores ≥ 28 at screening and baseline.
- Fluent in English.
- Provision of written informed consent/assent as previously described.
- Agrees to use one of the following method of birth control: complete abstinence from sexual intercourse, barrier (diaphragm or condom), or oral/injectable contraceptive.

Exclusion Criterion:

- Contraindication to an MRI scan (e.g., metal clips, braces or claustrophobia).
- Mood symptoms resulting from acute medical illness or acute intoxication or withdrawal from drugs or alcohol as determined by careful medical evaluation or rapid symptom resolution.
- Psychotic symptoms (i.e., hallucinations or delusions).
- Any lifetime history of a manic or hypomanic episode.

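### Prediction 4 fits one metabolite-to-mood slope for both arms; if the slope exists only on omega-3, which the plan calls plausible, the indirect effect is about half the omega-3-arm value, so add an interaction sensitivity analysis

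*Combined protocol and SAP*

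**What the plan says.** In the combined protocol and SAP, section II.E.b (Data Analyses), Prediction 4 sets up a system of linear regressions with CDRS-R and other mood measures as outcomes, "with changes in metabolite levels as mediators and treatment group as an independent variable". Path coefficients are bootstrapped and judged at "adjusted $\alpha=0.017$ to control for multiple testing". Mediation counts as supported only if the treatment-to-metabolite path and the metabolite-to-mood path are both significant. The extent of mediation is then read from the direct effect. A non-significant direct effect is taken as consistent with complete mediation. If treatment also acts in ways the model leaves out, "the direct (i.e., residual) treatment effect may remain significant and the data would be said to support *partial mediation". The BIC comparisons remove paths from this model; none adds an interaction.

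Under Exploratory analyses, the same section plans a moderation ANCOVA and describes a pattern in which "an association between metabolite levels and mood symptoms exists in the omega-3 fatty acid group, but not in the placebo group". It adds: "Such an outcome is plausible because placebo response may occur due to mechanisms that are independent of those we hypothesize". That analysis is exploratory and uses a 0.05 threshold.

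Prediction 5(b) examines the metabolite-to-mood slope within the omega-3 arm at 0.017. The predictor in that model is change in red-cell omega-3, not randomised treatment.

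**The concern.** With no interaction term, the metabolite-to-mood coefficient is a weighted average of the two within-arm slopes. If only the omega-3 arm has a slope, the average dilutes it. The product of paths then understates the part of the omega-3 effect that runs through the metabolite, and what is missing is counted as direct effect, which the plan attributes to unspecified other actions of treatment. The metabolite-to-mood path also becomes harder to detect.

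Mediation is Aim 2 of the trial. The model used to answer it leaves out a pattern that the plan describes a few paragraphs later, and the analysis that does allow for the pattern does not alter the mediation estimates.

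**Working it through.** **No plan figure to reproduce.** The available text gives no power figure for the mediation test and no metabolite-mood correlation. One side check: 0.05 / 3 = 0.0167, which rounds to the stated 0.017.

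**Inputs from the documents**
- Section F.2: "We propose to randomize 30 subjects per treatment group, for a total of 60 subjects".
- Section F.2: "approximately 25% of patients will either discontinue study participation prior to completing study procedures or will not have usable MRS data". So 60 × 0.75 = 45 evaluable, taken as 23 omega-3 and 22 placebo.
- Alpha 0.017, taken as two-sided.
- Section F.2 regards "medium to large effect sizes of $d > 0.6-0.8$ to be clinically relevant". Applying 0.6 and 0.8 SD to the treatment effect on the metabolite is an assumption; 1.0 SD is added as a favourable case.

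**Assumed inputs.** One metabolite with equal variance in both arms; within-arm correlation r of 0.5, 0.6 or 0.7 on omega-3 and 0 on placebo; mood change scaled to unit within-arm variance, so the omega-3 slope equals r.

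**Step 1: indirect effect.** Let a be the treatment effect on the metabolite, and b1 and b0 the omega-3 and placebo slopes. The expected shared slope is w × b1 + (1 − w) × b0, with w = (23 − 1) / (23 + 22 − 2) = 22/43 = 0.512. With b0 = 0 and a = 1.0:

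| r on omega-3 | Indirect, shared slope (a × w × b1) | Indirect, omega-3-arm slope (a × b1) |
|---|---|---|
| 0.5 | 0.26 | 0.50 |
| 0.6 | 0.31 | 0.60 |
| 0.7 | 0.36 | 0.70 |

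Simulation of 20,000 trials per scenario gives the same values to within about 0.01.

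**Step 2: direct effect.** Let m0 be the mean placebo metabolite change. With no other treatment action, the total effect is b1 × (m0 + a), so the shared-slope direct effect is b1 × (m0 + (1 − w) × a). For equal arms (w = 0.5), a = 0.8 and b1 = 0.5:
- m0 = 0: 0.5 × 0.4 = 0.20
- m0 = +0.5 SD: 0.5 × 0.9 = 0.45 (simulated 0.46)
- m0 = −0.5 SD: 0.5 × (−0.1) = −0.05 (simulated −0.05)

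The halving in step 1 does not depend on m0; the size of the direct effect does.

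**Step 3: power for the metabolite-to-mood path** (simulation, alpha 0.017, t tests standing in for the bootstrap)

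| r on omega-3 | Shared slope | Omega-3-arm slope | Difference (points) |
|---|---|---|---|
| 0.5 | 25% | 50% | 25 |
| 0.6 | 37% | 72% | 35 |
| 0.7 | 51% | 89% | 38 |

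Repeat runs move these by about one point.

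**Step 4: power under the two-path rule.** The treatment-to-metabolite path is a two-sample t test with noncentrality a × √(23 × 22 / 45) = 3.35 × a, giving power of about 33%, 58% and 80% at a = 0.6, 0.8 and 1.0. The two tests are close to independent, so the joint loss is roughly that power times the step 3 difference:
- a = 0.6: 0.33 × 25 to 0.33 × 38 = 8 to 13 points (simulated 8-13)
- a = 0.8: 0.58 × 25 to 0.58 × 38 = 15 to 22 points (simulated 15-23)
- a = 1.0: 0.80 × 25 to 0.80 × 38 = 20 to 30 points (simulated 19-30)

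**Step 5: the opposite case.** With r = 0.5 in both arms and a = 1.0, the shared slope is unbiased and stronger: path power about 87% against 58%, and SD of the indirect effect about 0.21 against 0.25.

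**Step 6: the planned interaction test.** At 0.05, its power in the omega-3-only scenarios is about 37-71%.

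Multiple metabolites and regions were not modelled.

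**The case against.** The strongest reply is that the plan already looks where it should. Prediction 5(b) is a numbered prediction that tests the omega-3-arm slope at 0.017. In a simulation assuming a red-cell-to-metabolite correlation of about 0.3, its power was 46%, 72% and 90% at r = 0.5, 0.6 and 0.7, against 49%, 73% and 89% for the slope from an interaction model. The moderation ANCOVA tests the interaction directly. This stands: the arm-specific slope would not go unexamined. What neither analysis yields is the indirect effect of randomised treatment computed with that slope.

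Three stronger readings are tempting, and the documents do not support them.

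- **That the mediation test loses 25 to 38 points of power.** That is the loss for one path, under correlations the documents do not supply. The plan requires both paths, and at the effect sizes it names the loss is 8 to 23 points.
- **That the plan expects an omega-3-only slope.** It says plausible, in an exploratory paragraph. Prediction 4(b) is stated without reference to arm, and the plan also allows that metabolite change marks improvement whatever the treatment, which is a shared slope.
- **That partial mediation would often be declared wrongly.** The plan labels by significance and reports no proportion mediated. Among simulated trials passing both paths with zero mean placebo metabolite change, the direct effect was significant in only about 1-5% at 0.017 and 4-11% at 0.05.

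It is also fair that half is relative to a definition: with unequal slopes the indirect effect is a × b1, a × b0 or something between, depending on whose slope is used. Reporting both versions meets that point.

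**Conclusion.** The concern holds in limited form. The Prediction 4 model assumes a common slope that the plan elsewhere says may not be common. If the slope exists only on omega-3, arms are near equal and metabolite variances match, the reported indirect effect is about half of the one defined by the omega-3-arm slope. The remainder goes into a direct effect whose size also depends on mean placebo metabolite change. The power figures are conditional on assumed correlations of 0.5 to 0.7, 45 evaluable patients and alpha 0.017, and should be quoted as ranges.

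The main exposure is a diluted estimate and a missed metabolite-to-mood path, more than a false label of partial mediation. If slopes are equal, the planned model is the better one, so it should not be replaced. This is a cheap improvement to make before analysis, not a flaw that invalidates Prediction 4.

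**What to change.** In section II.E.b:

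1. Keep the shared-slope path model as the Prediction 4 test at 0.017.
2. For each mediator, pre-specify one sensitivity analysis that adds treatment × metabolite change to the mood equation. Report with bootstrap intervals the indirect effect (treatment effect on metabolite × omega-3-arm slope) and the matching direct effect (treatment difference at the mean placebo metabolite change), so that the two sum to the total effect.
3. State that this analysis does not replace the primary test and does not decide whether Prediction 4 is supported.
4. Report both versions whatever the interaction p-value. With power of about 37-71%, that p-value is too weak to choose between models.
5. Where the two versions differ, qualify any statement of complete or partial mediation accordingly.

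The cost is plan wording and one extra term per mediator, with no new data. The downside is the lower precision of the companion when slopes are equal (working, step 5), which is why it sits beside the planned model and not in its place.
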